Primary outcomes include process outcomes. The primary outcome of interest is PrEP uptake. Rates of PrEP uptake will be compared in the first 6 months between those in the intervention and control arms; a sensitivity analysis will be conducted to examine de-identified rates of PrEP uptake among others during the same timeframe. Other process outcomes of interest will investigate the reliability of the strategy to 1) deliver an educational PrEP decision

STU#: STU00217596

guide to women with increased vulnerability to HIV, 2) engage those individuals in the PrEP decision guide, and 3) schedule patients for a dedicated PrEP visit

Secondary outcomes include psychosocial outcomes. In post-pilot interviews, we will obtain the following measures. Differences between intervention and control groups will be explored.

The main secondary outcome is PrEP knowledge measured about 2-6 weeks after randomization to the intervention (receiving the materials) or the control (delayed receipt).

Perceived Risk of HIV. We will use the 8-item Perceived Risk of HIV scale to assess how vulnerable an individual feels to HIV. The scale was developed in the United States and attention was paid to health literacy. Response options vary for each item, though they are measured on a 4-point Likert scale.

PrEP Knowledge. We will use a scale created by our team, drawing from the scale previously created by Welsh for use with men.

PrEP Attitudes. PrEP attitudes will be assessed using a recently developed scale developed that includes 5 items, each measured on a 5-point Likert scale (1=strongly disagree to 5=strongly agree).

[figure not shown]
Health Literacy. We will assess health literacy skills via the Newest Vital Sign (NVS).

Participants will be asked to view a nutrition label and to answer 6 questions about how they would interpret the information. Scores are classified as high likelihood of limited literacy (0-1), possibility of limited literacy (2-3), and adequate literacy (4-6). The NVS has a high correlation with the Test of Functional Health Literacy in Adults and includes both reading and numeracy items.

Health Activation. Patients' engagement in their child's healthcare will be measured using a modified version of our team's 10-item Consumer Health Activation Index (CHAI). Response options are a Likert scale; linear transformation is used to put total scores onto a 0-100 scale, with higher numbers indicating greater activation.

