Our pilot study will be conducted at select Northwestern Medicine (NM) primary care, after receiving committee approval to inform potentially eligible women about PrEP by providing them with an educational material that will educate them on PrEP and provide decision support for those who might be interested in speaking with a dedicated PrEP provider about PrEP use. We will not be altering the standard of care; rather, we will be providing additional materials and support to those who may benefit. A recent EHR data pull indicates there are ~1400 female patients who are potentially eligible for PrEP in primary care. For evaluation purposes, these women will be 1:1 randomized to either: 1) immediate receipt of the EMC² PrEP strategy as part of the intervention group or 2) a delayed receipt of the EMC² PrEP educational materials as part of the control group. Immediate receipt may take place over a rolling period over the course of several months. This not only ensures everyone receives the strategy, but it also allows for a practical rollout that respects the clinic bandwidth. Randomization will occur using a random number generator. EHR data will be evaluated in aggregate to determine, for example, how many women received the PrEP decision guide, opened it, interacted with it, scheduled a dedicated PrEP visit and/or received a PrEP prescription. Data will also be evaluated during the acute period to compare those who immediately received the EMC² PrEP strategy, and those who were delayed in their receipt of the strategy.

PROCEDURES INVOLVED:

Study Design Overview

To achieve our objectives, mixed-methods research will be conducted to adapt, pilot, and disseminate the EMC² strategy for use in PrEP decision making among women in primary care.

Aim 1: Adaptation Phase

During the Adaptation Phase (Aim 1), we will: 1) obtain clinician and EHR analyst input from various committee approval meetings; 2) develop and refine the content of the PrEP decision guide via cognitive interviews with the target audience (N=15), and 3) construct the technological build for both the decision guide and the post-visit treatment initiation questionnaire. A Scientific Advisory Board (N=3) will provide guidance on the strategy and intervention content throughout this process.

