3. Participants will also be asked to view, review, and provide feedback on the draft PrEP decision guide material, including the message informing patients they've received the PrEP decision guide in MyChart and an embedded video.
4. Interviews will focus on the material and are not intended to collect personal information.

[figure not shown]
Procedures for the EHR build. Drs. [name] and [name] (Co-I) will work with NM analysts to build the materials within Epic. Under their direction, clinical informatics staff will build and pilot the strategy in the electronic test environment and implement the strategy after any needed troubleshooting.

Procedures for engaging with the Scientific Advisory Board. During the adaptation phase, we will iteratively work with a Scientific Advisory Board via email and/or videoconferencing platforms for the purpose of obtaining additional scientific guidance on our strategy and content. The board will be comprised of three individuals whose combined expertise will include infectious disease, PrEP, and informatics. The study team will identify individuals with demonstrated expertise through our professional networks at multiple academic institutions and Centers for Aids Research. *This board will also function as a 'mini DSMB'.*

Trial registration. The study protocol will be registered with ClinicalTrials.gov.

Aim 2: Pilot Implementation Phase (Months 10-19)

Procedures for implementing the pilot study. For this 'development of concept' pilot study, the EMC² PrEP strategy will be sent to eligible women over a 6-month period at Northwestern primary care practices.

Approximately 1400 women have been identified as potentially PrEP eligible based on a previous EHR data pull. Women will be randomized 1:1 to either *immediately* receive the EMC² PrEP strategy (intervention; n=700) or a *delayed* invitation (control arm; n=700). In this manner, all patients will have eventually have the opportunity to receive EMC² PrEP materials. Process outcomes may be collected on all these ~1400 women. 100 women per arm will be identified and a

STU#: STU00217596

post-pilot interview conducted to further evaluate intervention effects.

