Procedures for post-pilot interviews (N=200). To further explore intervention effects, the study RC will interview 200 participants approximately 2-6 weeks after they have received the materials or after they have been randomized to the control arm. This includes interviewing 100 participants randomized to the EMC² PrEP strategy intervention arm and 100 randomized to the control arm (delayed invitation).

These patients will participate in an interview lasting ~1 hour. This interview will take place either in person, over the phone, or via a secure videoconferencing platform, depending on patient preferences and the status of the COVID-19 pandemic. However, the last 50 intervention arm participants will have their interviews conducted over a secure videoconferencing platform so that the RA can show them the EMC² PrEP education materials (the PDF and the video) before initiating the interview questions. Cameras will be turned off and there will be no recording. The purpose is just to ensure these participants have had a chance to view the materials before they answer study interview questions. All questions will be verbally asked by the RA as if the participant were on the phone and data will be captured in REDCap per usual. Interviews with both intervention arm (N=100) and control arm (N=100) patients will include quantitative measures assessing perceived risk of HIV, as well as PrEP knowledge, attitudes, stigma, and information sources. Additionally, we will measure health literacy, health activation, and basic demographic information.

Patients enrolled in the intervention arm (N=100) will also complete measures of satisfaction, specific to each strategy component.

Aim 3: Dissemination activities (Months 20-22)

These activities will be the last to occur. First, to obtain feedback from clinicians at a participating NM primary care practice(s), we will speak with clinic staff during an available business meeting after the completion of the pilot study to gauge their reactions to the approach. We will specifically aim to identify clinic-level barriers to implementation of the EMC² PrEP strategy.

The Northwestern research team will then solicit opinions about how best to implement this type of study at AllianceChicago affiliated clinics. To achieve this the research team will speak with current clinic administrators, prescribing providers, or EHR analysts within FQHCs affiliated with AllianceChicago or AllianceChicago itself (N~15).

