We will first seek a waiver of HIPPA for recruitment and to be able to send eligible women the PrEP guide via their MyChart. Then, these potential post-pilot interview participants will be identified via the EDW for post-pilot interviews. This list of patient names, medical record numbers, phone numbers, address, and date of birth will be compiled in a report that can be securely accessed and reviewed by study staff. Reports will be run approximately 2 or more times weekly to identify eligible patients.

Similar to the cognitive interviews, recruitment will be done by the RC via telephone rather than by mailing letters. Patients will be called via telephone within approximately 15 days of receiving the materials (randomization to the intervention arm) or randomization to the control arm. Trained RCs will contact identified patients and if they are interested in participating or learning more about the study, the RC will obtain verbal permission to ask the patient a brief series of questions to verify eligibility. If eligible, RC will obtain electronic informed consent. They will then initiate the post-pilot interview or schedule the interview for a time that is convenient to the participant.

COMPENSATION FOR PARTICIPATION IN RESEARCH ACTIVITIES

Study Activity	Payment Amount
Aim 1: Key Informant interviews with clinicians and administrators	\$100
Aim 1: Cognitive interviews with patients	\$30
Aim 2: Post-pilot interviews	\$45

All compensated participants will be paid at the completion of their interview via the PNC Stored Value Visa Card program (physical gift card) or via the Northwestern Visa Prepaid Card program (virtual gift card). At the end of their interview, participants will be asked which payment type they prefer.

WITHDRAWAL OF PARTICIPANTS

There are no anticipated circumstances when a participant would be withdrawn from the study without their consent. Interviews are all conducted at single time-points, therefore participants will not be asked to participate in any subsequent interviews.

RISKS TO PARTICIPANTS

STU#: STU00217596

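### The plan does not fix one starting date for the 2-6 week interview window; if women are randomized once before a rolling send-out, the two arms are interviewed in different calendar periods

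*Combined protocol and SAP*

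**What the plan says.** Three places in the combined protocol and SAP set the timing of the interview or of the call that leads to it.

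- Procedures Involved, post-pilot interviews: women are interviewed about 2-6 weeks "after they have received the materials or after they have been randomized to the control arm". The two arms have different anchors.
- Study Endpoints: the main secondary outcome is "PrEP knowledge measured about 2-6 weeks after randomization to the intervention (receiving the materials) or the control (delayed receipt"). Here the intervention anchor is randomization, with receipt in brackets as if it were the same event.
- Recruitment Methods, post-pilot interviews: women are telephoned "within approximately 15 days of receiving the materials (randomization to the intervention arm) or randomization to the control arm". Receipt and randomization are again equated.

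Three other places describe how randomization and sending relate.

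- Study Intervention(s): "A recent EHR data pull indicates there are ~1400 female patients who are potentially eligible for PrEP in primary care". These women are randomized 1:1, and "Immediate receipt may take place over a rolling period over the course of several months", partly to respect what the clinic can absorb.
- Procedures Involved, Aim 2: the strategy "will be sent to eligible women over a 6-month period", with 700 women per arm.
- Study Timelines, Aim 2: the strategy is switched on for the intervention arm for 6 months, and then for the control arm.

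The randomization method is a random number generator. No date, batch structure or link to the send-out is given. Data Management and Confidentiality plans a t test, chi-squared test or Fisher test for knowledge by arm, and multivariable logistic models with arm as the main covariate. No calendar-time or batch term is named.

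**The concern.** The two anchors amount to the same thing only if each intervention woman is randomized on the day she is sent the materials. The text about an identified list and a rolling send-out leaves room for a different sequence: everyone randomized at the start, controls interviewed within weeks, and intervention women interviewed whenever their turn to be sent the guide comes.

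Under that sequence, anything that changes over the rollout would differ between arms for reasons unrelated to the guide. Examples are outside information about PrEP, clinic activity, interviewer experience, and women who start PrEP or leave the practice before their send date. The Background itself notes that other forms of PrEP are under trial and some are nearing approval, so a change in general awareness is conceivable.

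The outcome at stake matters. Study Endpoints calls PrEP knowledge the main secondary outcome, and the Quantitative Methods text lists it among the primary outcomes.

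**Working it through.** The documents give no effect size, standard deviation or power for knowledge, so there is no planned figure to reproduce. The only internal check is 1400 / 2 = 700 per arm, which agrees with the plan.

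**Inputs from the documents**
- Interview window: 2-6 weeks after the anchor.
- Send-out: several months, with 6 months (26 weeks) as the stated period.
- Interviews: 100 per arm.
- Significance level: 0.05, taken as two-sided because the plan does not say.

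**Assumptions**
- Sends are spread evenly over W weeks.
- The interviewed women are spread evenly over the sends.
- The delay from anchor to interview is uniform on 2-6 weeks (mean 4).

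**Reading A: one randomization date, sending afterwards.** Control interviews fall in weeks 2-6. An intervention interview falls at R + U, with R uniform on 0 to W and U uniform on 2 to 6.
- Mean gap between arms = W/2.
- Share of intervention interviews after week 6 = P(R > 6 − U). Since 6 − U is uniform on 0 to 4 with mean 2, this is 1 − 2/W for W of at least 4.
- Latest intervention interview = week W + 6.

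| Rollout | W (weeks) | Mean gap (weeks) | After control window closes | Latest interview |
|---|---|---|---|---|
| 2 months | 8.7 | 4.35 | 1 − 2/8.7 = 77% | week 14.7 |
| 3 months | 13 | 6.5 | 1 − 2/13 = 85% | week 19 |
| 4 months | 17.4 | 8.7 | 1 − 2/17.4 = 89% | week 23.4 |
| 6 months | 26 | 13 | 1 − 2/26 = 92% | week 32 |

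A simulation with 1,000,000 draws gave the same values.

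**Reading B: randomization in batches at sending.** Both arms have the same anchor distribution, so the expected gap is 0 weeks for any W.

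**What a gap could do (illustration only).** With 100 per arm, the standard error of a standardized difference is √(2/100) = 0.141 SD. If calendar drift shifted the arms by b SD with no true effect, two-sided type I error would be Φ(b/0.141 − 1.96) + Φ(−b/0.141 − 1.96).
- b = 0.05: 0.054 + 0.010 = 6.4%.
- b = 0.10: 0.105 + 0.004 = 10.9%.
- b = 0.15: 0.184 + 0.001 = 18.6%.

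The documents support no particular value of b, nor its sign.

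**A limit on any common anchor.** The control arm is switched on after 6 months. If control index dates are spread evenly over 26 weeks and all controls are switched on at week 26, an interview falls after switch-on when index date + U exceeds 26. The probability is mean(U)/26 = 4/26 = 15%. A common anchor therefore needs a rule for late-indexed controls.

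**The case against.** The best reply is that the sentences which define the endpoint and the recruitment call both equate randomization to the intervention with receipt. On that wording the clocks coincide and the gap is zero.

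Some operational text also suits a rolling process. Eligibility reports are run about twice a week or more. Under a single randomization date, one research coordinator would have to complete 100 one-hour control interviews in about four weeks, or 25 a week. The figure of about 1400 is a count of potentially eligible women from a data pull, which need not be the list as randomized. Interviewees might also come mainly from early sends, which would shrink any gap. The by-arm knowledge tests are labelled exploratory. Interviewees must already meet the criterion of not currently using PrEP, and eligibility is verified by telephone in both arms.

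Most of this stands. A reader might infer from the interview procedures alone that the arms will be interviewed months apart and that the knowledge result is biased by a definite amount. The documents do not support that: they nowhere state a single randomization date, and they give no trend in knowledge.

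The reply does not show that the anchors agree. The interview procedures use different wording from the other two sections, and the rollout text is compatible with randomization long before receipt. The telephone check tests PrEP use at the time of contact, and that time could itself differ by arm. The exploratory label carries limited weight when the same section also names knowledge a primary outcome.

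**Conclusion.** The plan is ambiguous on a point that decides whether the knowledge comparison is concurrent. Under batch randomization at sending there is no gap. Under a single randomization date and an even send-out, the mean gap is about 4 weeks for a 2-month rollout and 13 weeks for a 6-month rollout, with 77% and 92% of intervention interviews after the control window has closed. These figures rest on even sends and on interviewees spread evenly over them.

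The bias that would follow cannot be sized from the documents. An assumed shift of 0.05-0.15 SD would raise type I error from 5% to about 6-19%, and that range is illustrative only.

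This is a gap to close before interviewing, with medium confidence that it affects the conduct of the trial. It is not a demonstrated bias.

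**What to change.** Reconcile Study Endpoints, Study Intervention(s), the post-pilot interview procedures and Recruitment Methods so that one anchor applies to both arms. State when randomization takes place relative to sending. Either of two rules will do:

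1. Randomize in batches at the time of sending, so that the date of randomization is the anchor for both arms.
2. If the list is randomized at once, assign every woman in both arms a random send week at that time. For controls it serves only as an index date.

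Under either rule:
- count the 2-6 week window from that date in both arms;
- apply the existing check on current PrEP use at that date in both arms;
- interview the two arms in parallel through the rollout;
- record the interview date, so that the analysis can adjust for batch;
- send no control the materials before her interview. Either hold back sending to late-indexed controls chosen for interview, or end control interview selection early enough that the window closes before switch-on.

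The cost is one extra column in the randomization list, a few sentences of text, and a short delay in sending to some controls if that option is used. If women are already randomized in batches at sending, what remains is a sentence saying so and the rule for late controls.

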To date, the EMC² strategy has been adapted and implemented in a variety of contexts, from higher-risk medications in primary care to knowledge and safe use of opioids in the Emergency Department (See **Table 1**). However, key components of this strategy address many of the well-documented barriers to PrEP uptake in primary care. Importantly, EMC² also promotes patient-provider discussion and decision-making, which will become increasingly important as potential new options for PrEP (e.g. long-acting pills, injectables, implants) may soon become available.

Table 1. EMC² Strategies Developed by Our Team

R01DK103684	Addressing Higher Risk Medications in Primary Care . Our team developed and is currently evaluating an EMC ² strategy to promote safe use of higher-risk medications for chronic conditions in primary care. This strategy utilized EMC ² core components (BPA, print materials, IVR reports) in Centricity EHR.
R18HS023459	Promoting Safe Opioid Use in the Emergency Department . Members of our team evaluated the use of an adapted EMC ² approach in an ED to support safe opioid use. This strategy used low literacy print materials generated via Epic EHR as well as educational, unidirectional text messaging.
PO4500987425	Educating and Monitoring Patient Understanding and Use of Newly-Prescribed Diabetes Medications . Members of our team have used a patient portal-based EMC ² approach to inform patients about risks surrounding higher-risk diabetes medications in academic, endocrinology and primary care settings.

For this study, we propose to adapt the current EMC² to provide quality improvement to the participating clinics'. The improved activities will:

- identify, via the EHR, female patients who have increased vulnerability to HIV
- educate pre-identified patients about PrEP using an interactive, health literacy-appropriate educational tool delivered via the patient portal
- facilitate scheduling of a dedicated PrEP clinic visit with an advanced practice nurse and/or physician for potentially eligible and interested patients

STUDY ENDPOINTS:

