Acceptability of the Strategy. Using 5-point Likert scale response options (1=very unsatisfied to 5=very satisfied), intervention participants will be asked to rate their satisfaction with various strategy components, including the materials, the dedicated PrEP visit, and the clinic follow-up activities.

Demographic Characteristics. We will collect a range of sociodemographic characteristics on the patient. This includes, but is not limited to: age, race/ethnicity, marital status, household income, and insurance status.

STUDY INTERVENTION(S) / INVESTIGATIONAL AGENT(S):

The Figure below provides an overview of key intervention activities.

Briefly, EMC² PrEP will help: 1) identify female patients in primary care who are at increased vulnerability to HIV due to prior suspected or confirmed bacterial STIs; 2) identified patients will receive an interactive, and educational PrEP decision guide via the patient EHR portal (they may also receive up to 3 reminders via the EHR portal to view the decision guide); 3) those who are interested in learning more about PrEP will be directed to schedule a dedicated visit with a dedicated PrEP provider; 4) during which PrEP options will be discussed and prescribed as appropriate.

STU#: STU00217596

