- 7) have no severe, uncorrectable visual, hearing or cognitive impairments that would preclude study consent or participation.

For the pilot study (**Aim 2**), we will randomize women who are potentially eligible for PrEP (N~1400; n=700 per arm) to intervention (the EMC² PrEP strategy) and control arms (delayed receipt of PrEP education materials). This is similar to a quality improvement activity. To be eligible to receive the EMC² PrEP strategy, participants must:

- 1) be an adult cisgender woman (age 18+) identified in the EHR who:
- 2) be HIV negative,
- 3) have received two or more tests in the past 12 months for chlamydia, gonorrhea and/or syphilis,
- 4) and/or have received a positive diagnosis for at least one of those sexually transmitted diseases (STIs) in the past 6 months;
- 5) are seen at the participating Northwestern Medicine practice(s);
- 6) have an active MyChart account;
- 7) not be currently using PrEP;
- 8) did not participate in the Aim1 cognitive interviews.

To be enrolled in post-pilot interviews (**Aim 2, N=200; n=100 per arm**), women must additionally (in addition to pilot study eligibility criteria):

STU#: STU00217596

- 1) speak English as their primary language; and
- 2) have no severe, uncorrectable visual, hearing or cognitive impairments that would preclude study consent or participation.
- 3) The last 50 intervention arm participants will also need to have access to videoconferencing platform (e.g. Zoom) so that they may view the PrEP education materials (the PDF and the video) before answering the interview questions.

For dissemination activities* (**Aim 3**), we will consult with key informants affiliated with AllianceChicago to explore study expansion. Participants in these consultations will be:

- 1) current clinicians and/or clinic staff from the participating NM site(s)
- 2) current clinic administrators, prescribing providers, or EHR analysts within an FQHC partnering with AllianceChicago or AllianceChicago itself

*Aim 3 Dissemination Activities are not considered human subjects research as these individuals are only providing information that will improve the intervention and/or inform the development of a standard operating protocol; no information will be collected about the participants themselves.

VULNERABLE POPULATIONS

We will not include any vulnerable populations in this research.

PARTICIPANT POPULATION(S)

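### PrEP knowledge is compared by arm, but staff show the materials to only the last 50 of 100 intervention interviewees just before the questions, so the difference cannot be attributed to portal delivery alone

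*Combined protocol and SAP*

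**What the plan says.** The Background says the strategy will "educate pre-identified patients about PrEP using an interactive, health literacy-appropriate educational tool delivered via the patient portal". The Study Intervention(s) section agrees: "identified patients will receive an interactive, and educational PrEP decision guide via the patient EHR portal".

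Study Endpoints sets the timing of the knowledge measure: "The main secondary outcome is PrEP knowledge measured about 2-6 weeks after randomization to the intervention (receiving the materials) or the control (delayed receipt"). For the interview measures generally it adds: "Differences between intervention and control groups will be explored". Quantitative Methods (under Data Management and Confidentiality) instead lists PrEP knowledge beside PrEP uptake as a primary outcome, so its status differs between sections.

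The Aim 2 interview procedures say: "To further explore intervention effects, the study RC will interview 200 participants approximately 2-6 weeks after they have received the materials", or after randomization for controls, with 100 women per arm. They then state that "the last 50 intervention arm participants will have their interviews conducted over a secure videoconferencing platform so that the RA can show them" the PDF and the video before the questions begin. The reason is given openly: "The purpose is just to ensure these participants have had a chance to view the materials before they answer study interview questions". The eligibility criteria for the post-pilot interviews add a condition for this group only: "The last 50 intervention arm participants will also need to have access to videoconferencing platform". No showing is described for the first 50 intervention interviewees or for the 100 controls.

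Quantitative Methods plans knowledge comparisons by study arm, multivariable logistic models with arm as the covariate of main interest, and a comparison of women who did and did not interact with the guide. Neither it nor Study Endpoints nor the Study Intervention(s) section gives a split, flag, covariate or sensitivity analysis for the two halves of the intervention interviews.

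**The concern.** The two halves of the intervention sample answer the knowledge questions under different conditions. The first 50 were sent the guide through the portal some weeks earlier and may or may not have opened it. The last 50 were sent the same guide and are also shown the content minutes before the questions. For them, part of any knowledge gain may be immediate recall produced by the interview procedure, which is not part of the strategy as defined.

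A single 100 v 100 comparison averages these two conditions. It estimates neither what portal delivery achieves nor what the materials achieve once shown. Aim 2 seeks preliminary efficacy of the strategy and Aim 3 builds a standard operating protocol for spreading it to other clinics, so whether portal delivery itself raises knowledge is a question the pilot should be able to address.

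The other measures from the same interviews (perceived risk, attitudes, stigma, information sources, and satisfaction with the materials) are exposed to the same mixing.

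**Working it through.** **Inputs from the protocol.** 200 interviews, 100 per arm; last 50 intervention interviewees shown the materials, so 100 - 50 = 50 not shown; t tests for continuous variables; significance level 0.05; about 700 women per arm for uptake.

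**Assumptions.** The protocol gives no effect size, SD, power or sample-size derivation for knowledge, so there is no figure to reproduce. I take normal scores with SD 1, a two-sided test, portal effect p, and a showing that adds v for each of the last 50. I also assume no calendar or selection difference between the halves.

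**Step 1: what the pooled contrast estimates.**
0.5 × p + 0.5 × (p + v) = p + v/2.

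**Step 2: p = 0, so portal delivery does nothing.** Simulated rejection rates, 200,000 replicates per scenario:

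| v (SD) | Pooled difference (SD) | Pooled 100 v 100 significant | First 50 v controls | Last 50 v controls |
|---|---|---|---|---|
| 0 | 0 | 5% | 5% | 5% |
| 0.2 | 0.10 | 11% | 5% | 21% |
| 0.4 | 0.20 | 28% | 5% | 63% |
| 0.6 | 0.30 | 54% | 5% | 93% |
| 0.8 | 0.40 | 78% | 5% | >99% |
| 1.0 | 0.50 | 92% | 5% | >99% |

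Hand check at v = 0.4: the mixture has variance 1 + 0.4²/4 = 1.04, so SE = sqrt(1.04/100 + 1/100) = 0.143. Then 0.20/0.143 = 1.40, and the chance of exceeding 1.96 is about 29%, against 28% simulated.

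**Step 3: both effects present.** With p = 0.2 and v = 0.4, the pooled difference is 0.2 + 0.4/2 = 0.40 SD, twice the portal effect. The split gives 0.20 SD for the first 50 and 0.60 SD for the last 50.

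**Step 4: precision cost of splitting.** The detectable difference at 80% power is approximately (1.96 + 0.84) × sqrt(1/n1 + 1/n2); exact values are from the noncentral t. The 95% CI half-width is the t quantile × sqrt(1/n1 + 1/n2).

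| Comparison | Detectable, normal approx. (SD) | Detectable, exact (SD) | CI half-width (SD) |
|---|---|---|---|
| 100 v 100 | 0.396 | 0.398 | 0.279 |
| 50 v 100 | 0.485 | 0.488 | 0.342 |
| 50 v 50 | 0.560 | 0.566 | 0.397 |

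**Step 5: reach into uptake.** Interviews at about 2-6 weeks fall inside the 6-month uptake window. At most 50/700 = 7% of intervention women receive the extra exposure.

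**The case against.** The showing is disclosed, with its purpose, in a development-of-concept pilot whose arm differences are mostly described as exploratory. That stands, and it limits the weight of the point. It does not settle the analysis, because the protocol explains why the showing is done but not how it is handled. The low weight also cannot rest on knowledge being secondary, since Quantitative Methods lists it as primary.

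The endpoint text describes the intervention condition as receiving the materials, and no section promises attribution to the portal alone. The investigators may want to know what the materials do once seen. That is a legitimate question, but the pooled figure does not answer it either, whereas reporting both halves serves both questions.

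The halves are not randomized subsets. They differ in recruitment order and in the videoconference criterion, so the split contrasts are not clean. This stands as a limitation of the remedy; pooling leaves those differences in place and hides them.

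The guide-interaction comparison may already be protected, because the Study Intervention(s) section has EHR data show who opened and interacted with the guide. That is the natural reading. However, that section describes aggregate counts and Quantitative Methods names no source, so one clarifying sentence is still worthwhile.

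A reader might also infer three stronger things that the protocol does not support:
- **That viewing was supervised or assured.** Cameras are off and the stated aim is only a chance to view, so the accurate description is that materials were shown at interview.
- **That the test's type I error is inflated.** If neither portal delivery nor the showing has an effect, the pooled test rejects in 5% of trials.
- **That the uptake result is compromised.** It is drawn from about 1400 women and touched only as in step 5.

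**Conclusion.** The point holds as one of attribution. Followed as written, the by-arm knowledge result is a 50:50 mixture of portal delivery and portal delivery plus materials shown at interview, and a difference cannot be credited to portal delivery alone. The distortion is half of whatever the showing adds (v/2), which could be negligible or could double the apparent effect. The protocol gives no basis for saying which, so the figures illustrate the mechanism and do not predict its size here. They also assume the same added effect in all 50, although some may already have viewed the guide.

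The uptake comparison is little affected. The information is recoverable if the plan says in advance how the halves will be reported. This is a cheap improvement to interpretation.

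**What to change.** Record the interview date and a shown/not-shown flag for every interview, and prespecify the following:

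- Report knowledge, perceived risk, attitudes, stigma and information sources with 95% CIs for (a) first 50 v controls, as the estimate for portal delivery, and (b) last 50 v controls, labelled as portal plus materials shown at interview. Adjust both for interview date, and state recruitment order and the videoconference criterion as limitations.
- Carry the same split into the multivariable knowledge model, with three levels: control, intervention not shown, intervention shown.
- Show the pooled 100 v 100 result alongside, labelled as a mixture.
- Report satisfaction with the materials separately for each half.
- In the guide-interaction comparison, define interaction from EHR portal data, do not count the staff showing as interaction, and analyse the last 50 separately or exclude them.

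The cost is analysis-plan wording and one data flag; no extra participants or interviews are needed. The loss is precision: the detectable difference at 80% power rises from about 0.40 to 0.49 SD, and the 95% CI half-width from about 0.28 to 0.34 SD. Date adjustment relies on control interviews being spread over both periods, and the protocol does not say when controls are interviewed. If only about 50 controls were effectively concurrent with each half (an assumption), the figures would be nearer 0.57 and 0.40 SD.
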